9.7.1.6.2 SECONDARY EFFICACY ANALYSES

The secondary analyses will be performed only if the primary analysis is significant. The treatment effect for E2609 50 mg/day versus placebo, for each secondary efficacy endpoint, will be tested using a sequential testing procedure at a significance level of 2-sided alpha =0.05, ie., any test will start only if the test with higher hierarchical order is significant. The final hierarchical order will be specified later in the statistical analysis plan before database lock.

Time to worsening of CDR scores by 24 months will be analyzed on the FAS using Cox regression model for treatment effect adjusting for randomization stratification factors. Time to worsening of a CDR score is defined as time from randomization to worsening of the CDR score (ie, the first worsening in 2 consecutive scheduled visits). For subjects whose CDR scores have not worsened by the end of study, the time to worsening of the CDR score will be censored at the date of last CDR assessment for these subjects.

Time to conversion to dementia for subjects who were not clinically staged as dementia at Baseline based on clinical diagnosis will be analyzed on the FAS using Cox regression model for treatment effect adjusting for randomization stratification factors. Proportion of subjects with dementia diagnosis at 24 months will be estimated using Kaplan–Meier method based on time to conversion to dementia based on clinical diagnosis. Time to conversion to

dementia for subjects who were not clinically staged as dementia at Baseline based on clinical diagnosis is defined as time from randomization to conversion to dementia based on clinical diagnosis. For subjects without clinical dementia by the end of study, the time to conversion to dementia based on clinical diagnosis will be censored at the date of last dementia diagnosis.

The rate of change over time (mean slope) based on change from baseline in the CDR-SB will be analyzed using linear mixed effects (LME) models for multivariate normal data derived from a random coefficient model (slope analysis), where the mean slope in each group depends on a continuous assessment time. The LME model will include baseline CDR-SB, randomization stratification variables, assessment time, and treatment group-by-assessment time.

The other continuous secondary efficacy endpoints as defined above will be analyzed using the same MMRM model as the primary efficacy analysis to compare E2609 50 mg per day versus placebo on the FAS, using baseline value corresponding to the response variable in the model.

The relationship between clinical changes at 24 months (CDR-SB, ADAS-cog₁₄, MMSE, and FAQ) and changes in each of the biomarkers (Amyloid PET, CSF t-tau and p-tau, vMRI) at 24 months will be evaluated using an ANCOVA model. Changes in clinical scales at 24 months will be the response variables and either continuous or categorical change of biomarkers will be independent variables. The ANCOVA model will also include baseline value for clinical scale as a covariate, randomization stratification variables, treatment group as factors, and other terms as appropriate.

9.7.1.6.3 EXPLORATORY EFFICACY ANALYSES

Time to change of concomitant AD treatment will be analyzed similarly to that for time to conversion to dementia based on clinical diagnosis. Time to change of concomitant AD treatment is defined as time from randomization to the first dose increase and/or initiation of treatment with AChEI or memantine after randomization. For subjects without any change of concomitant AD treatment by the end of study, the time to change of concomitant AD treatment will be censored at the date of last assessment of concomitant medication.

The proportion of subjects with any change of concomitant AD treatment at 24 months will be analyzed similarly to that for proportion of subjects with dementia diagnosis at 24 months.

The rate of change over time (mean slope) based on change from baseline in the NPI-10 item will be analyzed in a manner similar to that used for the rate of change over time (mean slope) based on change from baseline in the CDR-SB.

The analysis of the following exploratory efficacy endpoints will be performed to compare E2609 versus placebo using the appropriate prespecified statistical methods including MMRM model, analysis of covariance model (ANCOVA), etc. For each exploratory efficacy endpoint, the treatment effect for E2609 50 mg per day versus placebo will be tested at a significance level of 2-sided $\alpha = 0.05$.

- Change from baseline in NPI-10 item at 24 months

- Change from baseline in EQ-5D (subject self-reported, study partner self-reported, and subject measured by proxy) and QOL-AD (subject and study partner) at 24 months
- Change from baseline in Zarit's Burden Interview at 24 months

Additional analyses may be performed as needed.

9.7.1.7 Pharmacokinetic, Pharmacodynamic, Pharmacogenomic, and Other Biomarker Analyses

9.7.1.7.1 PHARMACOKINETIC ANALYSES

Safety Analysis sets will be used for individual E2609 plasma and CSF concentration listings. The PK Analysis Set will be used for the summaries of E2609 plasma and CSF concentrations.

A population PK approach will be used to characterize the PK of E2609. The effect of covariates (ie, demographics) on E2609 PK will be evaluated. The PK model will be parameterized for clearance (CL) and volumes of distribution. Derived exposure parameters such as AUC will be calculated from the model using the individual posterior estimate of CL and dosing history.

9.7.1.7.2 PHARMACOKINETIC-PHARMACODYNAMIC

The PK/PD relationship between CSF biomarker levels and plasma PK parameters or CSF concentrations of E2609 will be explored graphically and any emergent relationship will be explored through population PK/PD modeling. These PK parameters include maximum observed concentration (C_{max}), and $AUC_{(0-24)}$ derived from the population PK model. The PK/PD relationship between plasma PK parameters and CSF concentrations of E2609 with other biomarkers may also be explored using similar methods.

Additionally, the relationship between various PK parameters (eg, C_{max}) or CSF concentrations of E2609 and CDR-SB at 24 months, and the relationship between various PK exposure parameters or CSF concentrations of E2609 and the change from Baseline for 24 months in ADAS-cog₁₄, and the MMSE, will be explored graphically. Any emergent relationships will be explored through population PK/PD modeling. The relationship between exposure to E2609 and most frequent AEs will also be explored.

9.7.1.7.3 PHARMACODYNAMIC, PHARMACOGENOMIC, AND OTHER BIOMARKER ANALYSES

The analysis of the biomarker endpoints defined as below will be performed to compare E2609 versus placebo using the appropriate prespecified statistical methods including MMRM model, analysis of covariance model (ANCOVA), etc. These analyses will be conducted without adjustment for multiplicity or sequential testing. For each endpoint, the treatment effect for E2609 50 mg per day versus placebo will be tested at a significance level of 2-sided alpha = 0.05.

- Change from baseline in Amyloid PET SUVR composite at 24 months for brain amyloid levels

- Change from baseline in CSF biomarkers t-tau and p-tau at 24 months
- Change from baseline in CSF amyloid biomarkers A β (1-40), A β (1-42), and A β (1-x) at 24 months
- Change from baseline in total hippocampal volume at 12 and 24 months using vMRI
- Change from baseline in the preservation of connectivity on fMRI from predefined anatomical regions connectivity maps (eg, precuneus, inferior frontal sulcus)

The relationship between exposure (in CSF, plasma) of E2609 with potential biomarkers of Alzheimer's disease as deemed appropriate will be evaluated using appropriate statistical model with the continuous changes in biomarker at 24 months as response variables and exposure variables (in CSF, plasma) of E2609 as independent variables.

9.7.1.8 Safety Analyses

Evaluations of safety will be performed on the Safety Analysis Set. The incidence of AEs, out-of-normal-range laboratory safety test variables, abnormal ECG findings, and out-of-range vital signs, suicidality, along with change from baseline in laboratory safety test variables, ECGs, and vital sign measurements will be summarized by treatment group.

9.7.1.8.1 EXTENT OF EXPOSURE

The Duration of exposure to study drug will be summarized as cumulative extent of exposure in categories with 3-month increment. The cumulative number and percent of subjects in each applicable exposure category will be presented by treatment group. Duration of exposure will be summarized using descriptive statistics as well as by 3-month duration categories using counts. The number and percent of subjects within each duration category will be presented by treatment group. Overall exposure (number of subject-months) is defined as summation over all subjects' exposure durations and will be summarized by treatment group.

9.7.1.8.2 ADVERSE EVENTS

The AE verbatim descriptions (investigator terms from the eCRF) will be classified into standardized medical terminology using the Medical Dictionary for Regulatory Activities (MedDRA). AEs will be coded to the MedDRA (Version 19.0 or higher) lower level term closest to the verbatim term. The linked MedDRA PT and primary system organ class (SOC) are also captured in the database.

A TEAE is defined as:

- An AE that emerges during treatment within 4 weeks of the last dose of study drug, having been absent at pretreatment (Baseline) or
- Reemerges during treatment, having been present at pretreatment (Baseline) but stopped before treatment, or
- Worsens in severity during treatment relative to the pretreatment state, when the AE is continuous.

Only those AEs that are treatment-emergent will be included in summary tables. All AEs, treatment-emergent or otherwise, will be presented in subject data listings.

The TEAEs will be summarized by treatment group on the Safety Analysis Set. The incidence of TEAEs will be reported as the number (percentage) of subjects with TEAEs by SOC and PT. A subject will be counted only once within an SOC and PT, even if the subject experienced more than 1 TEAE within a specific SOC and PT. The number (percentage) of subjects with TEAEs will also be summarized by maximum severity (mild, moderate, or severe). The number (percentage) of subjects with TEAEs will also be summarized by relationship to study drug (Yes [related] and No [not related]).

The number (percentage) of subjects with treatment-related TEAEs will be summarized by SOC and PT. Treatment-related TEAEs include those events considered by the investigator to be related to study drug. The number (percentage) of subjects with treatment-related TEAEs will also be summarized by maximum severity (mild, moderate, or severe).

AEs will be summarized by the following subgroups: *ApoE4* status (positive or negative), prior treatment with AChEIs or memantine (no or yes), and clinical subpopulation (MCI due to AD or the early stages of AD).

The number (percentage) of subjects with TEAEs leading to death will be summarized by MedDRA SOC and PT for each treatment group. A subject data listing of all AEs leading to death will be provided. The number (percentage) of subjects with treatment-emergent SAEs will be summarized by MedDRA SOC and PT for each treatment group. A subject data listing of all SAEs will be provided. The number (percentage) of subjects with TEAEs leading to discontinuation from study drug will be summarized by MedDRA SOC and PT for each treatment group. A subject data listing of all AEs leading to discontinuation from study drug will be provided.

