In the MAD study, AEs of interest included relapse of orolabial herpes, viral respiratory tract infection, drug rash, and abnormal dreams. More details are available in the Investigator's Brochure. In summary, E2609 administered at doses of 200 and 400 mg was associated with reductions in CD4 (T helper cells), CD8 (cytotoxic T cells), and CD19 (B cells) counts at Day 8. These reductions were more clearly evident by Day 15, consistent with a treatment by time interaction in the statistical analysis. There was evidence that the lower doses of 50 to 100 mg also caused some reduction in CD4 lymphocyte counts by Day 15. Doses above 100 mg appeared to be associated with greater reductions in CD4 and CD8 lymphocyte counts, which occurred earlier in the treatment period compared with the effects of 25 to 100 mg doses. These effects on lymphocyte counts gradually resolved from Day 20 to Day 35, which were 6 and 21 days, respectively, after administration of the last dose of E2609 on Day 14. Reductions in CD4 and CD8 lymphocyte counts at doses of 200 and 400 mg to a level close to or less than the lower limit of normal (LLN) could be associated with increased risk of developing relapse of orolabial herpes or other infections.

In Study 003, a drug-drug interaction study, PK results showed that itraconazole (a potent inhibitor of cytochrome P450 [CYP] 3A4 and carboxylesterase-2 [CES2]) caused a mild

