9.5.4.1 Reporting of Serious Adverse Events

All SAEs, regardless of their relationship to study treatment, must be reported on a completed SAE form by email or fax as soon as possible but no later than 24 hours from when the investigator becomes aware of the event.

SAEs, regardless of causality assessment, must be collected up to 12 weeks after the last dose of study drug. All SAEs must be followed to resolution or, if resolution is unlikely, to stabilization. Any SAE judged by the investigator to be related to the study treatment or any protocol-required procedure should be reported to the sponsor regardless of the length of time that has passed since study completion.

The detailed contact information for reporting of SAEs is provided in the Investigator Study File.

For urgent safety issues, please ensure all appropriate medical care is administered to the subject and contact the appropriate study team member listed in the Investigator Study File.

It is very important that the SAE report form be filled out as completely as possible at the time of the initial report. This includes the investigator's assessment of causality.

Any follow-up information received on SAEs should be forwarded within 1 business day of its receipt. If the follow-up information changes the investigator's assessment of causality, this should also be noted on the follow-up SAE form.

Preliminary SAE reports should be followed as soon as possible by detailed descriptions including copies of hospital case reports, autopsy reports, and other documents requested by the sponsor.

The investigator must notify his/her IRB/IEC of the occurrence of the SAE in writing, if required by their institution. A copy of this communication must be forwarded to the sponsor, or its designee, to be filed in the sponsor's Trial Master File.

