Specified that history of ophthalmic shingles or history of ocular herpes simplex virus infection are exclusionary, in addition to active infections of ophthalmic shingles or ocular herpes simplex virus.	Added for clarification	Synopsis 
 Exclusion criteria Section 9.3.2
Removed “ocular” inflammatory disease requiring immunosuppressive or immunomodulatory therapy from exclusion criteria	Ocular therapy is permitted.	Synopsis 
 Exclusion criteria Concomitant Drug/Therapy Section 9.3.2 Section 9.4.7 Listing 2 of Appendix 2
Removed exclusion for significant abnormalities in laboratory tests or electrocardiogram (ECG) at Baseline assessment	Results from Baseline assessment will not be available at the Baseline Visit	Synopsis 
 Exclusion Criteria Section 9.3.2
Clarified that the exclusion of subjects with a prolonged QTcF interval is based on the central read of the Screening ECG.	Added for clarification	Synopsis 
 Exclusion Criteria Section 9.3.2

Revisions to Version 3.0

New version/date: Version 4.0/28 Jun 2017 (per Amendment 03)

Change	Rationale	Affected Protocol Sections
Specified that “short-term” concomitant use of benzodiazepines is permitted as specified in the protocol	Added for clarification	Synopsis 
 Concomitant Drug/Therapy Section 9.4.7 Listings 5 and 6 of Appendix 2
Specified that repeat testing for subjects who develop Grade 2 or greater lymphocytopenia should be performed as soon as possible, with the repeat blood sample drawn no later than 5 calendar days from the date of the original test result.	Added for clarification	Synopsis 
 Safety Assessments Section 9.3.3
Updated text describing monitoring adverse events (AEs) that may signal drug abuse potential, physical withdrawal or dependence; specified that monitoring will include the Treatment Period and the first 4 weeks of the Follow-up Period	Added for clarification and alignment with current US Food and Drug Administration (FDA) Guidance for Industry for “Assessment for Abuse Potential for Drugs”	Synopsis 
 Safety Assessments Section 9.5.1.5.1 Section 9.5.2 (Table 5) Section 9.5.4.3.1 Section 10 Appendix 3

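### The TEAE definition gives the 4-week post-dose window only to events absent at Baseline, so pretreatment events that return or first worsen after the last dose are left out of the AE and SAE summary tables

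*Protocol*

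**What the plan says.** Section 9.7.1.8.2 is worded identically, on this point, in both full texts of the protocol in the file (the text marked as revised per Amendment 01 and the unmarked text). An AE is treatment-emergent if it meets one of three conditions:

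1. New: "An AE that emerges during treatment within 4 weeks of the last dose of study drug, having been absent at pretreatment (Baseline) or"
2. Returning: "Reemerges during treatment, having been present at pretreatment (Baseline) but stopped before treatment, or"
3. Worsening: "Worsens in severity during treatment relative to the pretreatment state, when the AE is continuous"

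The section then says: "Only those AEs that are treatment-emergent will be included in summary tables". All AEs go into subject listings. The tables for deaths, SAEs and events leading to discontinuation are likewise restricted to treatment-emergent events, with all such events listed.

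In these texts Section 9.5.1.5.1 collects AEs from consent through Visit 15, and its AE criteria include exacerbation of an existing disease. For SAEs, Section 9.5.4.1 adds: "SAEs, regardless of causality assessment, must be collected up to 12 weeks after the last dose of study drug".

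The revision history for Version 4.0 (Amendment 03) records that the TEAE definition was changed to specify emergence on or after the start of study treatment. The Version 7.0 text of Section 9.7.1.8.2 is not in the file; only its table-of-contents entry is.

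**The concern.** The three limbs should describe one observation period, because they differ only in what the subject had before dosing. Here the end of the period depends on that history. Two subjects could have the same symptom on the same day after the last dose, and only the one with no pretreatment occurrence would be counted in the by-arm tables. The protocol gives no reason for the difference.

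The protocol itself treats the first weeks off drug as relevant to safety. Amendment 03 extended the follow-up of AEs that may signal abuse, withdrawal or dependence, and "specified that monitoring will include the Treatment Period and the first 4 weeks of the Follow-up Period". At stake is whether exacerbations of pre-existing conditions shortly after stopping can be compared between arms without reconstructing them from listings.

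**Working it through.** There is no figure to reproduce. The check is a literal classification of events, using the three limbs and the table rule in Section 9.7.1.8.2, the collection period in Section 9.5.1.5.1, the visit days in Table 3 and the eligibility rules in Section 9.3.2.

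**Is the period observed?** Table 3 puts Visit 13 on Day 729, Visit 14 on Day 757 and Visit 15 on Day 813. Taking Visit 13 as the end of dosing, 757 − 729 = 28 days (4 weeks) and 813 − 729 = 84 days (12 weeks). So the 4-week window ends at a scheduled visit, inside the AE collection period of the texts shown. The Version 7.0 synopsis, as amended by Amendment 05, collects new AEs for 4 weeks after the last dose in subjects who stop early, which still spans the window.

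**Where does an event starting in those 4 weeks go?**

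| Event with onset after the last dose | Limb met | In summary tables? |
|---|---|---|
| Absent at Baseline, first occurrence | New | Yes |
| Began on treatment, recurs or worsens after the last dose (absent at Baseline) | New | Yes |
| Present before treatment, resolved before dosing, returns after the last dose | None: the returning limb stops with treatment | No, listing only |
| Continuous since before treatment, first worsens after the last dose | None: the worsening limb stops with treatment | No, listing only |

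**Can the third row occur?** Yes. AEs are recorded from consent. Active infection within 4 weeks before randomization is an exclusion, but randomization may be put off for up to 4 weeks so that the infection can resolve. An infection recorded in screening and resolved before dosing is the case the returning limb describes.

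**Can the fourth row occur?** Yes. It is the cleanest case: a chronic condition that is stable on drug and worsens once drug is stopped.

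**An ambiguity in the third row.** Section 9.5.1.2.1 has sites record past herpes infections, including relapse frequency. The definition does not say whether such history makes an event present at pretreatment. If it does not, a later episode is new and is counted. If it does, the episode falls into the gap. The AE criteria in Section 9.5.1.5.1 use the same Baseline phrase when they treat recurrence of an intermittent condition not present at Baseline as an AE, which favours the first reading without settling it.

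**Wording of the new-event limb.** It joins two periods in one phrase: "An AE that emerges during treatment within 4 weeks of the last dose of study drug". The table above takes it to mean during treatment or within 4 weeks afterwards.

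**The case against.** The strongest reply is that this text has been superseded. The current protocol is Version 7.0, Amendment 03 changed this definition, and the current section cannot be read here. That stands as a limit on the conclusion. However, the log describes only a change to when the period starts; nothing shown says that the other two limbs gained the post-dose window.

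A second reply is that during treatment may be meant to include the 4 weeks in every limb. That may be the intention, but only one limb says so.

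A third is that other outputs cover part of the ground. Laboratory values are summarised by visit, and markedly abnormal values are identified from any postbaseline result. The Version 7.0 synopsis summarises possible drug-abuse signals by arm as a separate item. All AEs and SAEs are listed. This stands, so the loss is from the AE and SAE summary tables, not from the report.

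A reader might also infer more than the documents support:

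- **That herpes relapse in any subject with a history of herpes goes uncounted.** With no lesion at Baseline, the natural reading is that the event is new, and it is tabulated.
- **That rebound after stopping is lost in general.** It is lost only as a return or worsening of a pretreatment event.
- **That persisting immune effects make the gap serious.** Section 7.1 says lymphocyte effects "gradually resolved from Day 20 to Day 35, which were 6 and 21 days, respectively, after administration of the last dose", but it ties the possible infection risk to reductions at 200 and 400 mg. This trial gives 50 mg, and Section 7.1 reports only some CD4 reduction at 50 to 100 mg.
- **That the arm with more early stops loses more events.** Each subject has one 4-week window whenever drug is stopped, so differential loss is not shown.
- **That the 4 weeks, summed over subjects, measure the harm.** That sum measures uncovered time, not events lost.

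**Conclusion.** The point holds in a narrow form. In the text shown, two classes of event are recorded but left out of every AE and SAE summary table: pretreatment events that resolved and return in the 4 weeks after the last dose, and continuous pre-existing conditions that first worsen in those weeks. A new event on the same day is tabulated. The gap is at most 4 weeks per subject and affects only subjects with a qualifying pretreatment event. The number of lost events cannot be estimated from the protocol, and no bias between arms is demonstrated.

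This rests on a literal reading of the three limbs, on reading the new-event limb as running 4 weeks past the last dose, and on the Version 7.0 section having kept the end-points of the other two limbs. The last of these must be checked. It is a definitional fault worth correcting; nothing here shows that it would change the safety conclusions.

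**What to change.** First check the Version 7.0 text of Section 9.7.1.8.2. If the end-points still differ, define a TEAE as an AE that emerges, re-emerges or worsens in severity relative to the pretreatment state, from the first dose to 4 weeks after the last dose, with that one window for all three limbs. Add a sentence saying whether a condition recorded only as medical history counts as present at pretreatment.

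The cost is a few sentences and a small amount of extra tabulation. No new data are needed. AE percentages may rise slightly.

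An optional addition at small cost is a by-arm table of SAEs and deaths through the 12-week collection period. SAEs starting after the fourth week are collected and listed but not tabulated under the text shown. That is a coherent choice, so the extra table is an improvement and not the correction of an error.
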